PEPPI-5 and HCCQ will be analyzed as continuous variables, based on the summary score of the entire survey (PEPPI-5 scale 0 – 25, HCCQ scale 1-7). We will first analyze all respondents (patients and family members) together, and then separate respondents into patient and family outcomes.

OPTION5 will be analyzed as a continuous variable with a scale that goes from 0 – 100 based on consensus coding of each T0 transcript. This is a surgeon/patient/family score that cannot be stratified by respondent. We will compare the average score between intervention and control for the entire cohort.

Secondary outcomes: Aim-2: treatment received, well-being [PROMIS]

Treatment received will be defined as patients who had at least one major operation during the study period (identified on completion of T3 chart review).

We will also analyze this outcome according to the following classification scheme to characterize the treatment plan after meeting with a surgeon:

1. Plan for major surgery (includes plans where surgery is the treatment decision but additional tests are required)
2. Plan to not have surgery (includes a decision that no surgery will be pursued or other clear treatment plan – e.g., chemo)
3. Plan is unclear – returning to discuss later, needs more information

PROMIS: These measures will be analyzed by respondent type (patient/family), and measures will be analyzed separately dependent on time of reporting (T2 and T3).

Patient: Impact of illness – positive: continuous scale: 8-20

Impact of illness – negative: continuous scale: 8-20

Family member: SF Global Health Physical Score: continuous scale raw score: 4-20

Family member: SF Global Health Mental Score: continuous scale raw score: 4-20

Patient and family member: Anxiety 4a: continuous scale: 4-20

We will then restrict the analysis to patients who plan to have major surgery, and family members' outcomes for family members whose dyad patient has a treatment plan for surgery. We will then adjust the analysis for patients who had a major complication with surgical intervention.

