For all secondary outcomes after completing the ITT analysis, we will perform a restricted analysis as described in the additional considerations section above. Specifically, we will restrict the analysis by removing the dyads (patient and family member) based on the T0 transcript of the conversation with the surgeon, which confirms whether the patient discussed surgery with the surgeon and had a vascular or oncologic problem. Next, we will further restrict the analysis based on penetrance of the intervention based on the criteria described above.

Additional important outcomes

Family member presence: We plan to compare the proportion of patients who are accompanied by a family member or “like family” friend to the visit with the surgeon between the intervention and control group as receipt of the QPL prior to a visit with a surgeon may prompt patients to bring a family member with them to the consultation visit for additional decision-making support. This binary outcome variable (yes/no family member present) will be ascertained from the T0 transcript which clearly notes number of family members/friends. Family members do not need to be enrolled in the study to be counted as present. We will use ITT analysis as well as a restricted analysis (as described above) to analyze this outcome.

Consult duration: We will compare the median consult length at T0 between groups. This is not an effectiveness outcome but rather information that clinicians and patients might want to know in considering use of the intervention in their clinic. We will also compare the median consult length within surgeon (pre/post) to account for fairly wide variation in surgeon routine (some surgeons clearly spend

45-60 minutes with patients whereas others spend 7-15 minutes with patients). Given that surgeons will have been assigned randomly to intervention wave the incidence of pre/post measurements will not be evenly distributed and may be too variable to determine real differences.

Exploratory analyses

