There are several factors that might impact the effect of the intervention that we have described in our protocol for exploratory heterogeneity of treatment effect (HTE) analysis. These include insurance status (as a marker of socioeconomic status): we will use a binary variable defined by standard insurance (Medicare/private/supplemental) or (Medicaid, dual eligible, charity care, none). We will also consider oncologic indications for surgery as distinct from vascular (as identified in the T0 transcript). We will also consider extent of comorbid illnesses, stratifying patients by Charlson score and categorizing high, medium and low comorbidity.

We will perform additional analysis of OPTION 5 (shared decision making) scores, evaluating the variability in OPTION 5 scores before and after intervention, considering that these scores likely have more between surgeon variability than within surgeon variability. Specifically, we will estimate the correlation on the surgeon random effect pre- and post- intervention.

Aim-3

We will analyze qualitative data with directed content analysis⁴⁵ using a deductive theory-driven analytic framework to evaluate interpersonal and intrapersonal conflict and to compare the similarities and differences between both arms of the study. To enrich the coding process and attend to professional biases, we will include investigators with diverse clinical backgrounds (nursing, palliative care, surgery and patient advocacy). To gain understanding of the trajectory of the patient's story we will triangulate data sources by linking the audio tape of the initial surgeon-patient conversation and the patient's clinical history from chart review, with the follow-up interview. We have previously shown that surgeons see preoperative conversations as a significant event, a time when a two-way agreement is made whereby the surgeon commits to operating and the patient commits to endure potentially burdensome postoperative care.²⁷ We will use this understanding of surgical buy-in to code and analyze preoperative visit and postoperative interview transcripts with the goal of understanding how the contractual relationship that surgeons perceive is experienced by patients. We will explore how postoperative complications were discussed during the initial patient-surgeon interaction with and without the QPL and whether this interaction has impact on subsequent treatment decisions, interpersonal and intrapersonal conflict.

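### Consult length is compared by arm medians and by within-surgeon pre/post medians, and neither comparison separates the QPL from calendar time

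*Combined protocol and SAP*

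**What the plan says.** The SAP section on additional important outcomes gives two analyses of consult duration. The first is between arms: "We will compare the median consult length at T0 between groups". The second is within surgeon: "We will also compare the median consult length within surgeon (pre/post) to account for fairly wide variation in surgeon routine". The reason given for the second is that some surgeons spend "45-60 minutes with patients whereas others spend 7-15 minutes with patients". The SAP qualifies the outcome, "This is not an effectiveness outcome but rather information that clinicians and patients might want to know", and warns that the pre/post data may prove too variable to show a real difference. Neither analysis mentions wave or calendar time.

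The SAP's General Analysis Plan, placed under the heading for primary outcomes, uses generalised linear mixed models with a treatment indicator, a surgeon random effect and site-by-time indicators. The last are included to control secular trends within site.

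Two neighbouring outcomes are worded briefly. For OPTION5 the section on Aim 1 secondary outcomes says "We will compare the average score between intervention and control for the entire cohort". For family presence the SAP says "We plan to compare the proportion of patients who are accompanied by a family member". Neither sentence names a model.

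**The concern.** Surgeons cross over in one direction only. Each surgeon's intervention visits therefore come after that surgeon's control visits, and the intervention arm as a whole is later in calendar time. Randomising the order of crossover does not change this. If consult length shifts over two years for reasons unrelated to the QPL, both stated contrasts will show the shift as a QPL effect, or will mask an effect in the opposite direction. The SAP guards against this for its primary outcomes, but the consult-duration paragraph does not carry the safeguard over. By the SAP's own account, clinicians and patients may use this result when they consider the QPL for their clinic.

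**Working it through.** **Inputs.** From the published protocol: 40 surgeons, six 4-month waves (0 to 5), 8 surgeons crossing at each of waves 1 to 5 (Setting and design; Table 1), and 2 patients per surgeon per wave (Recruitment), giving 240 per arm. The planning range for the surgeon share of variance is 0.05 to 0.30 (Sample size and power calculation).

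**The plan's own figure.** The documents give no figure for consult length. As a check on the reconstruction, Table 1 was rebuilt surgeon by surgeon and the information-based variance computed with a surgeon random effect and site-by-time terms. At a surgeon share of 0.05 the standard error is 0.134 SD. With two-sided alpha 0.025 (z = 2.241), power is Φ(0.425/0.134 − 2.241) = 82.4% and Φ(0.5/0.134 − 2.241) = 93.2%. The published protocol states 82% and 93%. At a share of 0.30 the results are 84.5% and 94.4%.

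**Time gap between arms.** Patients by wave 0 to 5:

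- Intervention: 0, 16, 32, 48, 64, 80. Mean wave = (16×1 + 32×2 + 48×3 + 64×4 + 80×5)/240 = 880/240 = 3.67.
- Control: 80, 64, 48, 32, 16, 0. Mean wave = (64×1 + 48×2 + 32×3 + 16×4)/240 = 320/240 = 1.33.
- Gap: 2.33 waves, and 2.33 × 4 = 9.3 months.

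**Time gap within surgeon.** A surgeon crossing at wave k has control waves 0 to k−1, with mean (k−1)/2, and intervention waves k to 5, with mean (k+5)/2. The gap is 3.0 waves, or 12 months, for every k. Neither gap depends on whether 2 or 3 patients are enrolled per cell, provided enrolment is even.

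**What drift does.** Under a steady drift of b minutes per wave and no QPL effect, a difference in arm means is 2.33b and a within-surgeon difference is 3b. A null simulation (1,500 runs per setting) checked this for medians. Its assumptions are a mean of 30 minutes, a total SD of 15 minutes and a surgeon share of 0.30. The rank test is only an illustration, since the SAP names no test for this outcome.

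| Drift (min/wave) | Arm medians (min) | Within-surgeon (min) | Unadjusted rank test rejects at 5% | SAP model rejects at 5% |
|---|---|---|---|---|
| 0 | 0.0 | 0.0 | 10% | 4% |
| 0.5 | 1.2 | 1.5 | 20% | 5% |
| 1 | 2.4 | 3.0 | 40% | 5% |
| 2 | 4.7 | 6.0 | 86% | 4% |

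At surgeon shares of 0.05 and 0.5 the false differences are almost the same. With no drift the rank test rejects 6% and 15% of the time respectively. The SAP model's estimate averages about zero throughout.

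**Surgeon mix.** First-crossing surgeons supply 80/240 = 33.3% of intervention patients and 16/240 = 6.7% of control patients. For last-crossing surgeons the shares are reversed. A surgeon crossing at wave k has net weight (12 − 4k)/240 = (3 − k)/60 in the crude difference in means. The sum of squares is 8 × (4 + 1 + 0 + 1 + 4)/3600 = 0.0222, so chance imbalance has SD √0.0222 = 0.149 between-surgeon SDs. In total-SD units this is 0.033 at a share of 0.05 and 0.082 at 0.30, or 0.5 and 1.2 minutes if the total SD is 15. Its expected value is zero because crossover order is randomised.

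**Price of adjustment.** Crude SE = √(0.0222 × share + (1 − share) × 2/240).

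| Surgeon share | Crude SE (SD) | Adjusted SE (SD) |
|---|---|---|
| 0.05 | 0.095 | 0.134 |
| 0.30 | 0.112 | 0.1305 |
| 0.5 | 0.124 | 0.1135 |

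An SE that ignores surgeons is √(2/240) = 0.091 at every share, so it understates the crude variance.

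**The case against.** The best defence is that consult length is descriptive, carries no alpha and no named test, and is reported in minutes for practical use. The SAP already adds a within-surgeon comparison aimed at surgeon routine and warns about its variability. Nothing in the documents shows that consult length drifts. The size of the gap assumes even enrolment and 4-month waves, whereas the SAP's Study design section allows up to 3 patients per surgeon and waves longer than 4 months. Adjustment also costs precision over the planning range.

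All of this stands and limits the weight of the point. It does not close the gap. The within-surgeon comparison deals with surgeon habits and leaves time untouched. Nor can the general model be read into the paragraph, which names specific statistics and adds a separate step for surgeon variation that a surgeon random effect would have made unnecessary.

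A reader might infer three stronger things that the documents do not support.

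- **That OPTION5 and family presence are also planned as crude comparisons.** The sentences name a contrast and rule out no model. The General Analysis Plan sets the mixed-model framework. The published protocol's Quantitative analyses section extends it to secondary analyses, though without naming OPTION. The SAP's exploratory section expects that "these scores likely have more between surgeon variability than within surgeon variability" and continues: "Specifically, we will estimate the correlation on the surgeon random effect pre- and post- intervention". For family presence, the published protocol plans mediation models with surgeon random effects. An inflated false-positive rate for OPTION5 would belong to a test that the SAP does not specify.
- **That surgeon habits bias the arm comparison.** With randomised order they add chance imbalance and understated variance, not systematic bias.
- **That the mixed model is also more precise.** Of the shares worked out above, this is so only at 0.5.

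**Conclusion.** The point holds for consult length and calendar time, and it is minor. Under the planned schedule both stated contrasts absorb any drift, about 2.33-fold between arms and 3-fold within surgeon. The refinement meant to improve the comparison is thus the more exposed of the two. That intervention visits are later follows from one-way crossover. The exact gaps rest on even enrolment by wave, and their length in months rests on 4-month waves. The realised 222/221 split is given without a breakdown by wave. The minutes in the simulation are illustrative. Whether any drift occurred is unknown, so the documents do not show that the result will be wrong, only that the stated analysis could not tell drift from effect. For OPTION5 and family presence the issue is an unstated model, which calls for clarification only.

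**What to change.** In the consult-duration paragraph, take the between-arm estimate from the SAP's own model: treatment, surgeon random effect and site-by-time terms, with a confidence interval. Two forms would serve. A linear mixed model on log minutes gives a ratio of geometric means. A median regression with the same time terms, and an interval that respects surgeon clustering, stays in minutes. Keep the raw arm medians and the within-surgeon medians as description, and say that they are not adjusted for time. Add one sentence each to the OPTION5 and family-presence text stating that the General Analysis Plan framework applies (linear and logistic respectively).

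The cost is a few sentences in the SAP. No new data are needed, and the same model structure is already required for the primary outcomes. The statistical cost is the wider interval shown above for surgeon shares of 0.05 to 0.30. The log-scale form also changes the summary from a difference in medians to a ratio.

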The intervention effect will be tested in the framework of generalized linear mixed effects models^{42,43} with a treatment dummy variable, surgeon random effect and site-by-time dummy variables to control site-specific secular trends.

All models will be estimated and tested using SAS version 9.3 (SAS Institute, Cary, NC), specifically PROC MIXED and PROC NLMIX.

We do not plan to impute missing data if the rate of missingness is low. Currently, our rate of missingness is quite low: 97% of patients and 92% of family members have completed T1. For T2, 88% of patients and 86% of family members have completed the survey and for T3 87% of both patients and family members have completed their survey. We plan to exclude variables for which there is no response (rather than impute these variables). Although we have a small number of incomplete audio recordings, we will treat audio recordings where less than half of the encounter with the surgeon was captured (a total of 6 recordings) as completely missing and those with more than half recorded as complete. We will perform sensitivity analysis to test whether this small loss of data impacts our findings by comparing the outcomes with and without inclusion of audio recordings that are more than half complete.

Aim-1 primary outcomes [Question Counting, PEPPi-5]

Aim 1 has five primary outcomes and as such will be analyzed with a Type I error rate of $\alpha=0.01$.

For question counting, we consider four specific types of questions and evaluate them with ordinal categories:

- Number of OPTIONS questions asked by patients and family members (0, 1, 2+)
- Number of EXPECTATION questions asked by patients and family members (0, 1, 2+)
- Number of ADVANCE DIRECTIVES questions asked by patients and family members (0, 1+)
- Number of RISKS questions asked by patients and family members (0, 1, 2+)

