To cite: [name], [name], [name], *et al*. Navigating high-risk surgery: protocol for a multisite, stepped wedge, cluster-randomised trial of a question prompt list intervention to empower older adults to ask questions that inform treatment decisions. *BMJ Open* 2017;7:e014002. doi:10.1136/bmjopen-2016-014002

Received 23 August 2016

Revised 10 January 2017

Accepted 31 March 2017

ABSTRACT

Introduction Older patients frequently undergo operations that carry high risk for postoperative complications and death. Poor preoperative communication between patients and surgeons can lead to uninformed decisions and result in unexpected outcomes, conflict between surgeons and patients, and treatment inconsistent with patient preferences. This article describes the protocol for a multisite, cluster-randomised trial that uses a stepped wedge design to test a patient-driven question prompt list (QPL) intervention aimed to improve preoperative decision making and inform postoperative expectations.

Methods and analysis This Patient-Centered Outcomes Research Institute-funded trial will be conducted at five academic medical centres in the USA. Study participants include surgeons who routinely perform vascular or oncological surgery, their patients and families. We aim to enrol 40 surgeons and 480 patients over 24 months. Patients age 65 or older who see a study-enrolled surgeon to discuss a vascular or oncological problem that could be treated with high-risk surgery will be enrolled at their clinic visit. Together with stakeholders, we developed a QPL intervention addressing preoperative communication needs of patients considering major surgery. Guided by the theories of self-determination and relational autonomy, this intervention is designed to increase patient activation. Patients will receive the QPL brochure and a letter from their surgeon encouraging its use. Using audio recordings of the outpatient surgical consultation, patient and family member questionnaires administered at three time points and retrospective chart review, we will compare the effectiveness of the QPL intervention to usual care with respect to the following primary outcomes: patient engagement in decision making, psychological well-being and post-treatment regret for patients and families, and interpersonal and intrapersonal conflict relating to treatment decisions and treatments received.

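### The exploratory OPTION 5 variability analysis names only a pre/post correlation of surgeon effects, which does not give the size or direction of a change in variability

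*Combined protocol and SAP*

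**What the plan says.** The SAP section Exploratory analyses gives the aim of the additional OPTION 5 work as "evaluating the variability in OPTION 5 scores before and after intervention". The stated background is that "these scores likely have more between surgeon variability than within surgeon variability". The next sentence turns this into an analysis: "Specifically, we will estimate the correlation on the surgeon random effect pre- and post- intervention". No other statistic is named.

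Two other places bear on the point:

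- **Secondary outcomes: Aim-1.** The score is treated as continuous ("OPTION5 will be analyzed as a continuous variable with a scale that goes from 0 – 100"), and the planned comparison is of means: "We will compare the average score between intervention and control for the entire cohort".
- **General Analysis Plan.** The common model has a "treatment dummy variable, surgeon random effect and site-by-time dummy variables to control site-specific secular trends". That is one surgeon effect. No variance is specified separately for the periods before and after crossover.

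**The concern.** The aim is about variability, and the statistic is a correlation. A correlation has no scale, so it cannot by itself say whether surgeons became more or less alike after crossover. It is also a property of the surgeon effects alone, so the spread among patients of the same surgeon does not enter it.

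What is at stake is modest but relevant to this trial. The published protocol (appended), under Relevance and dissemination, suggests that lasting change in surgeon behaviour may contribute to the effect, and it directs dissemination mainly at surgeons. Whether the intervention narrows differences between surgeons in shared decision making is therefore worth knowing. If only the correlation is reported, a reader could not tell a trial in which those differences halved from one in which they stayed the same.

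**Working it through.** The documents give no variance, ICC or power figure for this analysis, so there is no figure of the plan's own to reproduce. The check is algebra, then simulation on the planned layout.

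**Inputs from the documents.** The published protocol's abstract states: "We aim to enrol 40 surgeons and 480 patients over 24 months". Its Table 1 has 8 surgeons crossing over in each of waves 1 to 5; its Recruitment section gives 2 patients per surgeon per wave and 12 per surgeon. A surgeon crossing in wave w has 2w visits before and 12 − 2w after. The totals are 8 × (2+4+6+8+10) = 240 before and 8 × (10+8+6+4+2) = 240 after. Realised recruitment in the SAP is 222 + 221 = 443, slightly smaller.

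**Assumptions, not in the documents.** Pre-intervention between-surgeon variance 1.2, within-surgeon variance 1.0, pre/post correlation 0.70.

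**Step 1: proportional change.** For positive a and b, corr(a·u_pre, b·u_post) = corr(u_pre, u_post). Residual variance does not appear. The ICC is between/(between + within); before the intervention it is 1.2/2.2 = 0.545.

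| Post-intervention scenario | Post ICC | True correlation | Median estimated correlation | Median estimated post ICC |
|---|---|---|---|---|
| No change | 1.2/2.2 = 0.545 | 0.70 | 0.73 | 0.54 |
| Between variance 1.2 to 0.3 | 0.3/1.3 = 0.231 | 0.70 | 0.73 | 0.22 |
| Between variance 1.2 to 2.4 | 2.4/3.4 = 0.706 | 0.70 | 0.72 | 0.69 |
| Within variance 1.0 to 0.25 | 1.2/1.45 = 0.828 | 0.70 | 0.69 | 0.82 |
| Within variance 1.0 to 2.0 | 1.2/3.2 = 0.375 | 0.70 | 0.74 | 0.36 |

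The last two columns come from 150 simulated trials per row, fitted by maximum likelihood with separate pre and post variances and without site-by-wave terms. The true correlation is held fixed, so its flatness is by construction. The simulation adds that, at this sample size, the estimated correlation stays flat while the estimated ICC follows the truth.

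**Step 2: independent surgeon shifts.** If u_post = u_pre + v, with v independent of u_pre and of variance τ², the correlation is √[1.2/(1.2 + τ²)].

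- τ² = 0.5: correlation √(1.2/1.7) = 0.84; SD ratio √(1.7/1.2) = 1.19.
- τ² = 1.2: correlation √(1.2/2.4) = 0.71; SD ratio √2 = 1.41.

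A simulation of equal-variance shifts (pre ICC 0.5, 60 runs) agreed: median SD ratio 1.41, median estimated correlation 0.73.

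Here the correlation moves with the variance, but does not identify the change. Take τ² = 0.5 and halve the result, u_post = 0.5(u_pre + v). The correlation is still 0.84, yet the post variance is 0.25 × 1.7 = 0.425 and the SD ratio is √(0.425/1.2) = 0.60. The same correlation goes with wider and with narrower differences between surgeons.

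**Step 3: can the ratio be estimated?** A second simulation used the Table 1 layout with site-by-wave terms, true correlation 0.95, a common residual variance and 200 runs per setting. The median estimated SD ratios were 1.01 and 0.51 (true 1 and 0.5) at a pre-intervention ICC of 0.5, and 1.02 and 0.52 at 0.3. The median estimated correlation was 0.95 to 0.97 throughout.

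A likelihood-ratio test of equal surgeon variances, with the SD halved, rejected in 96% of runs at ICC 0.5 and 64% at 0.3. With residual variance allowed to differ by period, rejection was 55% at ICC 0.3, 12% at 0.1 and 3% at 0.05. Those three rest on 60 runs each; the Monte Carlo standard error for 55% is √(0.55 × 0.45/60), about 6 points.

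**The case against.** The strongest defence has four parts.

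**The correlation is not blind to variability.** A reader might infer that it never moves when the spread changes. That goes too far: independent surgeon shifts raise the variance and lower the correlation (Step 2). What stands is that its value does not identify the size or direction of the change.

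**The plan sets no hypothesis that between-surgeon variability exceeds within-surgeon variability.** That clause is a premise. Given it, asking whether surgeons keep their own style is a coherent exploratory question. Nor does the plan state a test of zero correlation, or say that a value near 1 means no change in practice. Criticism of such a test or reading would be of something the documents do not contain.

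**Real effects would not all be lost.** If every surgeon rose equally, the planned comparison of average scores would be expected to reflect it. A model with two correlated surgeon effects also estimates both surgeon variances, so a narrowing would be in the output. This is right, but the plan does not commit to reporting them, and the single surgeon effect in the General Analysis Plan would have to be extended before a pre/post correlation exists.

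**The sentence may be loose wording for an ICC in each period.** The published protocol's sample-size section links a correlation among patients of the same surgeon to a surgeon-level random effect. A per-period ICC would come much closer to the aim. This reading is possible but less plain: that section, and the coder-agreement table in the SAP, use ICC terms where an ICC is meant, and the exploratory section does not.

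**Conclusion.** The point holds in a limited form. The aim is variability before and after the intervention. On its plain reading, the only named statistic measures whether surgeons keep their relative position. It is unaffected by proportional narrowing or widening and carries no information on within-surgeon variance. The planned comparison of means does not fill the gap.

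The algebra needs no assumed values. The sizes shown do: the variances, correlations and ICCs are assumptions, because the documents give none for OPTION 5. The 5% to 30% surgeon share cited for the power calculation is not specific to this score.

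A reader might infer that the OPTION 5 comparison is invalid or that a trial conclusion is at risk. The documents do not support that: the analysis is labelled exploratory, and no primary or secondary conclusion depends on it.

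**What to change.** Replace the sentence that names the correlation with text such as:

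> We will fit a linear mixed model for OPTION 5 with treatment, site-by-wave terms, correlated surgeon random effects for the pre- and post-intervention periods, and residual variance allowed to differ by period. As exploratory estimates, we will report the between-surgeon variance, within-surgeon variance and ICC in each period, and the post/pre ratio of between-surgeon SDs with a 95% CI. The pre/post correlation of surgeon effects will be reported as a measure of whether surgeons keep their relative ranking.

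If a per-period ICC was intended all along, the SAP should say so.

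The cost is a few lines of text. The model needed for the correlation already estimates both surgeon variances, and period-specific residual variance adds one parameter. The downside is precision: if surgeons account for a small share of the variance, the interval for the SD ratio will be wide and a test of equal variances will have little power (Step 3). The result should therefore rest on estimates and intervals, not on a significance test.
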